10.1 Purpose

The purpose of the reading process is for the readers to provide the BI-RADS assessment categories, probability of malignancy (POM) scores, recall scores, locations and types of any finding(s) on the eCRFs for their interpretation of the study cases; with FFDM images and DBT plus S-View images on the ASPIRE Bellus II workstation.

10.2 Conduct of the Reading Process

Following the successful completion of the reader training, the readers will independently review and score each of the image sets of the reader study case set. Each reader will work at a designated workstation and will independently perform two reads on all cases. Each reader will read each case both as a FFDM read, and a DBT plus S-View read on the ASPIRE Bellus II workstation. Each reader will read half the cases on FFDM and the other half of the cases on DBT **p**lus S-View during the first visit. The reader will then read the complementary FFDM and DBT plus S-View during the second visit. In order to minimize memory recall bias, the two reading visits will be separated by a memory washout period of approximately four weeks.

Interpretation of mammography images will be performed in a controlled environment with consistent lighting. The review workstations will be preloaded with the cases. The readers will be permitted to use standard softcopy imaging tools, and all routine post processing capabilities (e.g., magnification, windowing and leveling) will be permitted. Hotkeys will be provided on the workstations for consistency and accuracy of the reading process. The reading time allowed per case will not be limited. A lunch break will be offered during each reading session, and radiologists will be encouraged to take a 5-10 minute break each hour, as needed. Each reader will dictate their interpretations to a trained scribe, who will enter the dictation directly into the eCRF. Each reader will sign an attestation form verifying the documented information.

10.2.1 Core Reading Center

The reading process will be conducted at International HealthCare, LLC in Norwalk, CT.

10.2.2 Preparation of Cases for Interpretation

To maintain subject confidentiality, no identifying subject data will be displayed. Unique image identifiers associated with the case ID number will be visible on each image for tracking purposes. To maintain reader confidentiality, a unique ID number will be assigned to each radiologist participating in the pivotal reader study for entry on the CRFs. Information collected during the research study was reported in such a way that it precluded identification of any image acquisition centers' or study radiologists' performance.

10.2.3 Workflow for the Interpretation of Cases

The readers will be told that the samples of cases do not represent a standard screening population, and will be blinded to the actual distribution and nature of the set of images they will be asked to review. Readers will be masked to the reference standard and image acquisition interpretations (under protocol FMSU2013-004A) for each case. Readers will not have access to prior mammograms or other clinical information. All readers will perform their interpretations independently.

Each study reader will be randomly assigned to a unique reading order. All study readers will ultimately interpret all study cases in both FFDM, and DBT plus S-View formats. Readers will interpret the preloaded mammograms in their assigned order with the use of barcode scanner/barcodes.

General instructions for the readers are as follows:

- Do not record single punctuate or round calcifications and vascular calcifications, given the high prevalence of these benign findings and their low probability of cancer.
- Consider all views available from both breasts to determine if you would recall the case.
- For examinations with multiple findings, record the types and locations of all findings in the eCRF and/or a breast schematic diagram that divides each breast image into sections and image slice for DBT images. Record the finding locations beginning with the most suspicious lesion (up to three lesions per case).
- Provide a BI-RADS assessment category of 1 through 5 for each annotated finding.
- Provide a probability of malignancy (POM) for each annotated finding according to the guidance listed in Table 4 (below).

Probability of Malignancy (POM): POM is a 0 to 100 score assigned by readers to each suspicious finding, as their perception of the percentage chance that the suspicious finding might be malignant. To help the assignment of POM scores readers will be instructed to use the entire POM scale, with descriptions of POM values provided in Table 4 only as guidance:

Note: POM scores will be determined and analyzed separately from the BI-RADS assessment category.

POM Score (%)	Description
0-20	Negative/Benign
21–40	Probably benign
41–60	Possibly malignant
61–80	Probably malignant
81–100	Malignant

Table 4: Probability of malignancy (POM) guidance

Interpretation instructions for the readers are as follows:

The reader will complete the eCRFs for each case for the two reads. For each case on each read, the reader will first record whether there are mammographic findings. If the answer to this question is "no" the reader will be asked to confirm for this case: a BI-RADS assessment category of 1 or 2, a POM score following the POM guidance provided in Table 4, and recall decision of "no". If the reader answers "yes" to whether there are mammographic findings, the reader will be asked to confirm an initial BI-RADS assessment category of 0, and will then provide detailed information on each suspicious finding:

- Affected breast (right or left)
- Type (includes mass, asymmetry, and/or architectural distortion), microcalcifications, or mass with microcalcifications, or other
- "Forced" BI-RADS assessment category 1, 2, 3, 4, or 5
- POM score 0 through 100
- The reader will then be asked whether the case shall be recalled ("yes" or "no"), their forced BI-RADS assessment category (1, 2, 3, 4 or 5), and POM score 0 through 100.

A study scribe representing the sponsor will capture the radiologist's results on the eCRFs to ensure completeness.

In cases with mammographic findings, consistency of POM scores with BI-RADS assessment categories and recall decisions will not be forced – i.e. readers will be permitted to use the full range of POM scores for a finding (following the POM guidance provided in Table 4) no matter what BI-RADS assessment category they assign to it.

10.2.4 Reading Sessions with a Memory Washout Period

Each reader will read each case both as a FFDM read and a DBT plus S-View read, on the ASPIRE Bellus II workstation. Each reader will read half the cases on FFDM and the other half of the cases on DBT plus S-View during one visit. The reader will then read the complementary FFDM and DBT plus S-View during the second visit. In order to minimize memory recall bias, the two reading visits will be separated by a memory washout period of approximately four weeks.

Reading Session Order

- a. The selected cases will be randomly allocated into four (4) sets of 75 cases each, case subsets A, B, C, and D. Allocation will be balanced with respect to reference standard (cancer, benign, recall, and normal), and to the extent possible in the case sample, on presence of calcifications, breast composition (fatty or dense), and image acquisition site.
- b. Each study reader will be randomly assigned to a unique reading order.
- c. Each session has 300 cases that will be read: **150** FFDM cases and **150** DBT plus S-View cases for the two read visits.

	Session 1				Session 2					
Pat.	Pa	rt 1	Pa	rt 2		Pa	rt 1	Pa	rt 2	Reader
	Gr. 1	Gr. 2	Gr. 1	Gr. 2	_	Gr. 1	Gr. 2	Gr. 1	Gr. 2	
1	В	D	С	А	۱۸/	А	С	D	В	11, 17
	FFDM	DBT +	DBT +	FFDM	vv	DBT +	FFDM	FFDM	DBT +	
2	А	С	D	В	۸	В	D	С	А	10, 20
	FFDM	DBT +	DBT +	FFDM	A	DBT +	FFDM	FFDM	DBT +	
3	С	В	А	D	c	D	А	В	С	14, 21,
	FFDM	DBT +	DBT +	FFDM	3	DBT +	FFDM	FFDM	DBT +	24
4	D	А	В	С	ы	С	В	А	D	9, 19
	FFDM	DBT +	DBT +	FFDM	п	DBT +	FFDM	FFDM	DBT +	
5	В	D	С	А	\cap	А	С	D	В	8, 15
	DBT +	FFDM	FFDM	DBT +	0	FFDM	DBT +	DBT +	FFDM	
6	А	С	D	В		В	D	С	А	7, 16
	DBT +	FFDM	FFDM	DBT +	0	FFDM	DBT +	DBT +	FFDM	
7	С	В	А	D	т	D	А	В	С	12, 18
	DBT +	FFDM	FFDM	DBT +	I	FFDM	DBT +	DBT +	FFDM	
8	D	А	В	С		С	В	А	D	13, 22,
	DBT +	FFDM	FFDM	DBT +		FFDM	DBT +	DBT +	FFDM	23

Table 5: One Possible Experimental Design

Pat. = Pattern. Gr. = Group. Reader numbers begin with 7 to prevent confusion with reader numbers on the pilot study. DBT + = DBT plus S-View.

Interpretation Results: For each case, the readers are asked to provide two sets of results from two reading visits separated by a memory washout period. Each reader will read half the cases on FFDM and the other half of the cases on DBT plus S-View during the first visit. The reader will then read the complementary FFDM and DBT plus S-View during the second visit.

11. The Lesion Matching Process

11.1 Purpose

The purpose of the lesion matching process will be to determine if the location and type of a finding identified by the reader matches those of a malignant lesion annotated by the truther, i.e., correct lesion localization and type.

11.2 Qualification Criteria and Training for the Lesion Matcher

An expert not associated with diagnosing cases at the image-acquisition sites or serving as a reader interpreting images on this pivotal reader study will serve as the lesion matcher for this study. This expert may be an experienced, MQSA-qualified mammography technologist with an active license, or a board-certified radiologist that is MQSA-qualified for both FFDM and tomosynthesis; if the latter, this expert radiologist may be the same person as the truther.

Base qualification criteria: The base criteria for the lesion matcher are as follows:

- Has an active license as a breast mammogram technologist
- Has experience with clinical research in the GCP environment
- Or, Study truther (refer to truther qualifications in section 8.2)

**Training**: The lesion matcher will participate in a training session to ensure understanding of the ASPIRE Bellus II workstation, the protocol, the eCRFs, study processes, GCP, and the obligations entailed by study participation. Particular attention will be given to the lesion matching process.

11.3 Conduct of the Lesion Matching Process

11.3.1 Core Matching Center

Lesion matching will take place remotely, with results documented within the truther/lesion matching database.

11.3.2 Preparation of Cases for Lesion Matching

The lesion matcher will have access to both the reader's eCRF and the truther's eCRF. The eCRF and images contain the annotated information, such as Subject ID number, the finding location(s), and finding type(s) which are required for the determination of correct lesion localization. The matching is limited to cases with malignant lesions. For each case with cancer, the lesion matcher determines if the annotation by the reader matches with that made by the truther.

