11.3.3 Workflow for the Lesion Matching Process

The lesion matching process is limited to those cases with malignant lesions. Based on the case ID number on the truther's eCRF, the lesion matcher identifies the reader's eCRF with the same Subject ID number. The lesion matcher compares the finding location(s) and finding type(s) of the reader's eCRF and annotated images to those of the truther's eCRF, to

March	14,	2018
DOC-0	037	'878-A

determine if the reader made the correct lesion localization. The process will be repeated for each reader's eCRFs that have the corresponding Reader Sequence ID number to truther's eCRFs, and for every reader. The lesion matcher will record the lesion matching results on the eCRFs.

- For each truther's eCRF, identify and confirm the reader's eCRF that contains the corresponding Subject ID number and Reader Sequence ID Number
- Identify and match the location (breast, view, and if possible the section and/or slice) and type of finding(s) with those of the truther's eCRF
- Document the matching results on the eCRF

Note 1: To allow for the possibility of lesions located on breast section boundaries, the reader will get credit for correctly locating a lesion if the matcher determines that the annotations match even if an adjacent quadrant is recorded on the case report form. In this situation, we anticipate x/y coordinates to be within 2 centimeters and slice numbers to be within 10 slices. Readers will not get credit for correctly locating a lesion if the matcher determines that the annotations do not match, even if the same quadrant is recorded on the case report form; in this situation the x/y coordinates and/or slice numbers also usually would not match with the pre-specified tolerance. The lesion matching process will be supported by programmatic (computer) determination of whether x and y coordinates are within 2 centimeters; and whether slice numbers are within 10 slices.

12. Statistical Analysis

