3.6. Blinding / Masking

The readers will be told that the samples of cases do not represent a standard screening population, and will be blinded to the actual distribution and nature of the set of images they will be asked to review. Readers will be masked to the reference standard and image acquisition interpretations (under Fujifilm protocol FMSU2013-004A) for each case. Readers will not have access to prior mammograms or other clinical information. All readers will perform their interpretations independently.

4. Statistical Methods

Informed consent. By approving this SAP, Fujifilm confirms the following: All subjects whose images were acquired under FMSU2013-004A and selected for this study were consented. As part of the consent process, subjects agreed that image data and supporting documentation could be used for future research and investigations. Each reader will be consented before initiating the reader study.

Masking to protect identities. Study case identification numbers and study reader numbers will be assigned to all cases and readers, and used to protect their identities in statistical analysis and in reporting of results.

Statistician not blinded. Because the reader data on lesion locations only includes Slice for DBT, the statistician will not be blinded to reading condition.

General conventions: Descriptive summaries. Baseline descriptive summaries will include the distribution of demographic characteristics and clinical characteristics, including characteristics specific to malignant and, if appropriate, benign lesions. We also will provide summaries across readers of the per-subject number of findings, BI-RADS scores, POM scores, and per-subject recall scores, for the FFDM and DBT plus S-View readings. These may be crossclassified by, for example, presence of malignant lesions. Categorical variables (such as cancer type and breast tissue composition) generally will be summarized using frequencies and proportions or percentages, while continuous variables generally will be summarized using means and standard deviations (SDs), and/or medians and quartiles or ranges. Missing values generally will be reported as such in these descriptive summaries.

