4	5	6	6	5	4	4	5	6	6	5	4
7	8	9	9	8	7		8	9		8	7
20.			21.			22.			23.		
24. Lesion Location: N/A CC: X Y Slice (DBT Only)											
N/A MLO: X Y Slice (DBT Only)											

25. Comments:

VF1.0_9292017 DOC-0036589-A Page 3 10/9/2017

FUJIFILM Medical Systems U.S.A., Inc.	
PROTOCOL: FMSU2017-002A/B	Reader Study Form
Sequence ID #:	Date of Reading (mm/dd/yy):
INITIAL MAMMOGR	APHIC FINDINGS
1. Are there any mammographic findings in this patie	ent's exam? Yes No
2. Initial BI-RADS Score: 0 1 Negative	2 Benign Finding
3. If BI-RADS 1 or 2, please answer questions 3a and	3b:
3a. Overall, what is your estimated probability of malig	gnancy for this patient (0-100%)?
3b. Would you recall this subject? 🗌 Yes 🗌 No	
If BI-RADS 0, please complete the following questions	for up to 3 lesions:

VF1.0_09292017 DOC-0036587-A Page 1 10/9/2017

BIOSTATISTICS	CONSULTING,	LLC
---------------	-------------	-----

FUJIFILM Medical Systems U.S.A., Inc.

PRO	DTOCOL: FMSU2017-0024	VB Reader Study Form
	Sequence ID #:	Date of Reading (mm/dd/yy):
		LESION #1
4.	Affected breast:	Right Left
5.	What is the most suspicious f	inding type? (check all that apply):
	a. Mass d. Architectural Distortion	b. Asymmetry c. Calcification e. Other (please specify):

6 - 9. Mark an X at the location(s) of the lesion on the Mammogram:

R-C	ic l			Ŀ	CC	R-ML	D			Ľ	-MLO	
.1	2	3	3	2	1	1	2	3	3	2	1	
4	5	6	6	5	4	4	5	6	6	5	4	
7	8	9	9	8	7	7	8	9	9	8	7	
6.			7.			8.			9.			I
10. Lesion Location: N/A CC: X Y Slice (DBT Only)												
		N		MLO: X		Y		Slic	e (DBT (Only)		
11. Bas	ed on th	ne image	s review	ved, wha [at is you 3	r forced E	BI-RADS	S score fo	or this le	esion? (check one))
12. Wha	at is you	ır estima	ated prol	bability	of malig	nancy for	this le	sion (0-1	00%)?			
VF1.0_0 DOC-00												age 2 /2017

FUJIFILM Medical Systems U.S.A., Inc.	
PROTOCOL: FMSU2017-002A/B Reader Study Form	
Sequence ID #: Date of Reading (mm/dd/yy): WRKSTNID #:	
LESION #2 N/A	
13. Affected breast: Right Left	
14. What is the most suspicious finding type? (check all that apply): a. Mass b. Asymmetry c. Calcification d. Architectural Distortion e. Other (please specify):	
15 - 18. Mark an X at the location(s) of the lesion on the Mammogram:	
R-CC L-CC R-MLO L-MLO 1 2 3 3 2 1 4 5 6 6 5 4 7 8 9 9 8 7	
15 16 17 18	
19. Lesion Location: N/A CC: X Y Slice (DBT Only) N/A MLO: X Y Slice (DBT Only)	
20. Based on the images reviewed, what is your forced BI-RADS score for this lesion? (check one) 1 2 3 4 5	

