21. What is your estimated probability of malignancy for this lesion (0-100%)?	
VF1.0_09292017 Page DOC-0036587-A 10/9/20	

FUJIFILM Medical Systems U.S.A., Inc.	
PROTOCOL: FMSU2017-002A/B	Reader Study Form
Sequence ID #: WRKSTNID #:	Date of Reading (mm/dd/yy):
LESIO	N #3 N/A
22. Affected breast: Right	Left
23. What is the most suspicious finding type? (
24 - 27. Mark an X at the location(s) of the lesior	on the Mammogram:
R-CC 1 2 3 3 2 1 4 5 6 6 5 4 7 8 9 9 8 7	R-MLO L-MLO 1 2 3 3 2 1 4 5 6 6 5 4 7 8 9 9 8 7
24 25	26 27
28. Lesion Location: N/A CC: X	Y Slice (DBT Only) Y Slice (DBT Only)
29. Based on the images reviewed, what is your	r forced BI-RADS score for this lesion? (check one)
30. What is your estimated probability of maligr	nancy for this lesion (0-100%)?
VF1.0_09292017 DOC-0036587-A	Page 4 10/9/2017

BIOSTATISTICS	CONSULTING,	LLC
---------------	-------------	-----

FUJIFILM Medical Systems U.S.A., Inc.	
PROTOCOL: FMSU2017-002A/B	Reader Study Form
Sequence ID #:	Date of Reading (mm/dd/yy):
OVERALL PAT	TIENT RECALL
31. Overall, would you recall this subject?	No
32. Overall, what is your forced BI-RADS score for th	his subject? (check one) 4 5
33. Overall, what is your estimated probability of ma	lignancy for this subject (0-100%)?

VF1.0_09292017 DOC-0036587-A Page 5 10/9/2017

Lesion Matching Form

FUJIFILM Medical Systems U.S.A., Inc.

PROTOCOL: FN	ISU2017-002A/B
--------------	----------------

	Subject ID #:	Date of Review (mm/dd/yy):
1.	Image Type: FFDM D	BT plus S-View
2.	Reader Sequence Number:	
3.	Truther Lesion #1:	
	Reader Lesion #: 1 2 3 Not Seen	
4.	Truther Lesion #2 or NA:	
	Reader Lesion #: 1 2 3 Not Seen	
5.	Truther Lesion #3 or NA:	
	Reader Lesion #: 1 2 3 Not Seen	
6.	Comments:	

VF1.0_09292017 DOC-0036586-A Page 1 10/9/2017

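### The lesion matcher is not masked to the reader's POM, BI-RADS and recall, although the matcher's judgement sets the score of every cancer read in which a finding was recorded

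*Protocol*

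**What the plan says.** **Access.** Protocol 11.3.2: "The lesion matcher will have access to both the reader's eCRF and the truther's eCRF". The same section says the material contains the subject ID and "the finding location(s), and finding type(s) which are required for the determination of correct lesion localization". It lists no score among the things matching needs, and it does not say that scores are hidden.

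**What the reader form holds.** In SAP Appendix 1 each lesion section of the Reader Study Form records location and type, then asks "what is your forced BI-RADS score for this lesion? (check one)" and "What is your estimated probability of malignancy for this lesion (0-100%)". The last page asks "Overall, would you recall this subject", followed by the overall BI-RADS and POM. The Lesion Matching Form has no score field, but it opens with "Image Type: FFDM" or DBT plus S-View.

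**Who decides a match.** Protocol 11.3.3, Note 1: "the reader will get credit for correctly locating a lesion if the matcher determines that the annotations match even if an adjacent quadrant is recorded". The note also allows credit to be refused when the quadrants agree. A computer check of 2 cm in x/y and 10 slices supports the process.

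**Who is masked.** SAP 3.6: "Readers will be masked to the reference standard and image acquisition interpretations". Protocol 10.2.3 likewise covers readers only. SAP 4 and Protocol 12 state that the statistician is unblinded, and why. Protocol 11 and SAP 3.5 say nothing about masking the matcher.

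**What follows from a match.** Under Protocol 12.3.1 and 12.3.2 (SAP Tables 1 and 2), a matched cancer read takes the highest POM and BI-RADS among its matched findings, and its recall decision stands. A read with findings but no match takes the floor POM (0, or the reader's minimum in that modality), BI-RADS 1 and no recall.

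**The concern.** For the exposed reads the matcher acts as an outcome assessor. Someone who can see that a reader gave a borderline finding a POM of 85 and recalled the patient may credit it more readily than the same mark with a POM of 15. The decision then determines whether that POM enters the primary AUC. It can also change per-subject sensitivity (H4, H8) and cancer recall (H3).

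The plan explains openly why the statistician is unblinded but is silent on the one person who makes a judgement that changes scores. It describes no second matcher, no agreement check and no record of departures from the tolerance. Protocol 11.2 also allows the matcher to be the truther.

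If matching is carried out with scores in view, the protection cannot be restored afterwards without rematching.

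**Working it through.** **1. What matching needs, against what access allows**

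| Field on reader eCRF | Needed for location and type? | Withheld from matcher? |
|---|---|---|
| Breast, view, diagram section, x/y/slice | Yes | No |
| Finding type | Yes | No |
| Forced BI-RADS per finding | No | Not stated |
| POM per finding | No | Not stated |
| Overall recall, BI-RADS, POM | No | Not stated |

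Visibility of the scores is therefore an inference from unrestricted access to a form that contains them.

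**2. Which reads are exposed**

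Cancer reads per modality: 60 × 18 = 1,080. Those with no recorded finding keep the reader's own POM and BI-RADS whatever the matcher does. Exposed reads are those with at least one finding, and within them only those whose match is open to judgement. The documents give neither number. Sensitivity changes only if the disputed finding is BI-RADS 4 or 5, and cancer recall only if the overall decision was to recall.

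**3. The plan's own power, to obtain a scale**

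SAP 4.10 gives var = (2/R){σ²ab + σ²w + σ²c[1 − r1 + (R − 1)(r2 − r3)]}, with R = 18, σ²ab = 0.0004, σ²w = 0.0001, r1 = 0.53 and r2 − r3 = 0.02. It names a binormal approximation for σ²c without printing it. I assumed σ²c = 0.0099·exp(−a²/2)·[(5a² + 8)/60 + (a² + 8)/240] with a = 1.414·z(0.80) = 1.190, which gives σ²c = 0.001417.

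- var = (2/18){0.0005 + 0.001417 × 0.81} = 0.000183, so SE = 0.0135.
- With 17 df at one-sided 0.025, the critical value is 2.110 and the noncentrality is 0.05/0.0135 = 3.70. Power is 93.6%.
- Using A2 = 0.75 in the case variance gives 92.9%.
- SAP Table 4 states 92%. Both results are within 2 points, which is close enough for scaling. The power figure is not in dispute.

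**4. Illustrative shift in the AUC difference**

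Assumptions, none from the documents: a credited read outranks 90% of non-cancer reads; a floor read outranks 5 to 25% (ties counted half); f is the net share of the 1,080 cancer reads resolved differently between modalities. Shift = f × (0.90 − 0.25) to f × (0.90 − 0.05).

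| f | Net reads | AUC shift | Share of 0.05 margin | Shift / SE | One-sided error at the margin if it favours DBT plus S-View (nominal 0.025) | Power if it goes against (93.6% without) |
|---|---|---|---|---|---|---|
| 1% | 10.8 | 0.0065–0.0085 | 13–17% | 0.48–0.63 | 0.07–0.09 | 86–82% |
| 2% | 21.6 | 0.013–0.017 | 26–34% | 0.96–1.26 | 0.15–0.22 | 73–63% |

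The last two columns are noncentral t tail areas beyond 2.110 with 17 df, at noncentrality shift/SE and (0.05 − shift)/SE.

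**The case against.** **Nothing says the scores are shown.** Correct. Protocol 11.3.2 describes the content by its purpose, and Protocol 11.3.1 refers to a matching database whose display is not described. The build may already hide the scores. If so, one sentence settles the point; as written, nothing prevents their being seen.

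**Discretion is limited.** Largely true. Protocol 11.3.3 expects credited marks to fall within tolerance and refused marks usually to fall outside it. The two-way discretion concerns the coarse quadrant. The matcher must be independent of the readers and of the acquisition-site diagnosis, and is trained for the task. These limits narrow the risk, but the tolerance still does not decide the match, and departures from it need not be recorded.

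**Leniency towards high scores would act in both modalities.** This is the strongest statistical point, and it stands in part. Such a tendency partly cancels in the AUC difference. It does not cancel if borderline findings are more frequent, or carry different POMs, in one modality.

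**Modality cannot be hidden.** It stands. Slice exists only for DBT, and Image Type is on both the truther and matching forms. Withholding scores closes the score-driven route and leaves the modality route visible, which is why departures should be reported by modality. A reader might infer that the plan omitted a feasible masking to modality. The documents' own slice argument for the statistician shows otherwise.

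**The size is assumed.** It stands. The 1% and 2% differentials are inputs to the calculation, not findings.

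**Conclusion.** The point holds as a preventable risk of bias in a judgement step that sets the primary score for cancer reads with recorded findings. It should be fixed because the protection is nearly free and matching has no use for the scores.

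Three stronger readings are tempting and unsupported:

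- That the documents state the matcher sees POM, BI-RADS and recall. They grant access to the form and are silent on its display.
- That the matcher determines all 1,080 cancer reads per modality. Reads with no findings are untouched.
- That the primary comparison is biased by some fraction of the margin. The documents give no rate of discretionary matches, and part of any score-driven leniency would cancel between modalities.

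The figure of 0.0065 to 0.0085 per net 1% of cancer reads rests wholly on the assumed ranks of credited and floor reads. The direction is unknown. A differential against DBT plus S-View would cost the sponsor power, so masking protects both sides.

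**What to change.** 1. In Protocol 11.3.2 and SAP 3.5 and 3.6, state that the matcher sees only the linking subject and sequence IDs, breast, view, diagram section, x/y/slice, finding type and annotated images, with BI-RADS, POM and recall withheld.
2. State that matching results are locked before reader scores are merged.
3. Log each case in which the matcher departs from the 2 cm / 10-slice flag, and report the counts by modality.
4. State that the matcher cannot be masked to modality, because of slice.
5. While editing, reconcile Protocol 12.3.1 and 12.3.2, which in places say the truther determines the match, with Protocol 11.3 and SAP 3.5, which assign it to the matcher.

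**Cost.** A filtered data view, a few sentences and one short table. Sample size, alpha and planned power do not change.

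**Optional.** A supportive AUC using the programmatic flag in place of the matcher's decision. This is more than one extra run. The flag does not test finding type, and coordinates can be recorded as N/A for a view, so rules for both would have to be written first.
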